#### **9.2 Evaluation After Protocol Treatment**

All patients will be seen at 4 weeks after completion of protocol therapy.

For patients who go off protocol treatment with progressive disease (PD), follow-up will be required every 3 months to document ongoing toxicities related to protocol treatment (until resolved to < grade 2), late toxicities (including second malignancies), and death.

For patients who go off protocol treatment with CR, PR, or SD ongoing, follow-up will be required every 3 months to document relapse/progression, ongoing toxicities related to protocol treatment (until resolved to < grade 2), late toxicities (including second malignancies), and death (see Appendix I for investigations to be performed).

#### 10 CRITERIA FOR MEASUREMENT OF STUDY ENDPOINTS

#### 10.1 Definitions

Evaluable for toxicity. All patients will be evaluable for toxicity from the time of their first treatment with sunitinib.

### 10.1.2

10.1.1

Evaluable for response. All patients who have received at least two cycles of therapy and have their disease reevaluated will be considered evaluable for response (exceptions will be those who exhibit objective disease progression prior to the end of cycle 1 who will also be considered evaluable). Patients on therapy for at least this period and who meet the other listed criteria will have their response classified according to the definitions set out below (Eisenhauer E, 2009).

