### 10.2.5 RESPONSE

All patients will have their BEST RESPONSE on study classified as outlined below:

Complete Response (CR): disappearance of all target lesions. Pathological lymph nodes (whether target or non-target) must have reduction in short axis to < 10 mm.

Partial Response (PR): at least a 30% decrease in the sum of diameters of target lesions, taking as reference the baseline sum diameters.

Stable Disease (SD): steady state of disease. Neither sufficient shrinkage to qualify for PR nor sufficient increase to qualify for PD, taking as reference the smallest sum diameters while on study.

Progressive Disease (PD): at least 20% increase in the sum of diameters of target lesions taking as reference the smallest sum on study (includes baseline sum if that is smallest on study). In addition, the sum must also demonstrate an absolute increase of at least 5 mm. Appearance of new lesions will also constitute progressive disease. In exceptional circumstances, unequivocal progression of non-target lesions may be accepted as evidence of disease progression.

Response Criteria

Target	Non-Target	New	Overall	
Lesions	Lesions	Lesions	Response	
CR	CR	No	CR	
CR	Non-CR/Non-PD	No	PR	
CR	Not evaluated	No	PR	
PR	Non-PD or not all	No	PR	
	evaluated			
SD	Non-PD or not all	No	SD	
	evaluated			
Not all	Non-PD	No	NE	
evaluated				
PD	Any	Yes or No	PD	
Any	PD*	Yes or No	PD	
Any	Any	Yes	PD	

\* In exceptional circumstances, unequivocal progression in non-target lesions may be accepted as disease progression.

Note: Patients with a global deterioration of health status requiring discontinuation of treatment

without objective evidence of disease progression at that time should be reported as "symptomatic deterioration". Every effort should be made to document the objective progression even after discontinuation of treatment.

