#### 11.0 STATISTICAL CONSIDERATIONS

### 11.1 Objectives and Design

This is a phase II study to investigate the efficacy of sunitinib in patients with advanced paraganglioma/ pheochromocytoma. The protocol will accrue up to 28 response evaluable patients. In order to minimize the expected number of patients treated in the event that the regimen proves to be very disappointing or very successful, a multistage design will be used for each cohort for patient accrual (Fleming T 1982).

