### 11.2 Primary Endpoints and Analysis

The **primary end point** will be clinical benefit rate (CBR) which will be defined as either a partial response (PR) complete response (CR) or stable disease (SD) for  $\geq 12$  weeks. This will be measured using the Response Evaluation Criteria in Solid Tumors (RECIST) criteria.

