### 11.3 Sample Size and Duration of Study

Stage 1 of accrual: 14 response evaluable patients will be entered in the first stage. Using response hypotheses of H0 < 5% and Ha > 20%, we would reject the drug at the end of the first stage of accrual no response was seen. Otherwise, additional 14 patients will be accrued to the cohort.

Stage 2 of accrual: Additional 14 patients will be accrued. We would accept the drug as active if three or more responses (as defined by the CBR) are observed from 28 patients accrued.

Significance level and power: The procedure described above test the null hypothesis that the response rate is 5% versus alternating hypotheses that the response rate is 20%. The significance level (i.e., the probability of rejecting H0 when it is true) is  $\alpha$ =0.14 and the power (i.e., the probability of deciding the regimen is active) is 0.92 when true response rate is 20%. The expected sample size with this design is 28.

Accrual and duration of study

The estimated monthly accrual for this study is 1-2 patients a month. Thus, patient accrual is expected to be completed within 12-48 months. Additional time is required to allow the response data to mature.

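### The primary response rates are taken only in patients who complete two cycles and are re-evaluated, which overstates benefit among all treated patients

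*Combined protocol and SAP*

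**What the plan says.** **Who counts for response.** Section 10.1.2: "All patients who have received at least two cycles of therapy and have their disease reevaluated will be considered evaluable for response". The only exception is patients with "objective disease progression prior to the end of cycle 1 who will also be considered evaluable". The sentence after it limits response classification to patients treated for at least that period who also meet the other criteria.

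**Who counts for toxicity.** Section 10.1.1 takes everyone: "All patients will be evaluable for toxicity from the time of their first treatment with sunitinib".

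**What is counted.** Section 11.1: "The protocol will accrue up to 28 response evaluable patients". Section 11.3: "14 response evaluable patients will be entered in the first stage". The primary endpoint in section 11.2 is CBR: CR, PR, or SD lasting 12 weeks or more. Overall response rate (CR plus PR) is secondary.

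**What does not fit.** Section 10.2.5 says "All patients will have their BEST RESPONSE on study classified as outlined below", and the final decision rule in section 11.3 refers to 28 accrued patients without the word evaluable. Neither says how a patient without a response assessment is scored. Section 10.2.5 also sets apart patients whose general decline forces them to stop: those "without objective evidence of disease progression at that time should be reported as" symptomatic deterioration. The exception for objective progression does not cover them.

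Section 11 contains no analysis of CBR or response rate in all treated patients, and no replacement rule.

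**The concern.** A cycle is six weeks, so two cycles take 12 weeks. The first scheduled imaging is at the end of cycle 2 (Trial Summary, On Treatment Evaluations; section 9.1). To enter the denominator a patient must therefore largely reach the point at which stable disease becomes a success. Two groups drop out of it:

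- **(a)** patients who stop for toxicity, withdraw, die or have symptomatic deterioration without objective progression before two cycles, including during cycle 1;
- **(b)** patients whose progression is found on an unscheduled scan in cycle 2, before two cycles have been received. These are documented failures, yet they meet neither the rule nor its exception.

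Progression documented in cycle 1, or first seen at the scheduled week-12 scan, stays in and counts as failure.

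Because the 14 and the 28 are counted in evaluable patients, those left out would in effect be replaced. The reported rate would then depend on how many patients cannot tolerate the drug, and tolerability is the trial's second objective. Because sections 10.1.2, 10.2.5 and 11.3 disagree, two analysts could also report different primary rates from the same data.

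**Working it through.** **1. The plan's own figures.** Inputs from section 11.3: stage 1 n = 14, stop if there are no responses; total n = 28, active if there are 3 or more; rates 5% and 20%; stated alpha 0.14 and power 0.92.

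P(active) = Σ over x = 1 to 14 of Bin(x; 14, p) × P(Bin(14, p) ≥ max(0, 3 − x)).

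- p = 0.05: 0.3593 × 0.1530 + 0.1229 × 0.5123 + 0.0301 = 0.148
- p = 0.20: 0.1539 × 0.8021 + 0.2501 × 0.9560 + 0.5519 = 0.915
- p = 0.50: 0.9999

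Power agrees with the stated 0.92 to rounding. Alpha is 0.148 against a stated 0.14, a separate small discrepancy on which this point does not depend.

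**2. Rate reported in evaluable patients.** Let p be the rate in all treated patients, d the share excluded and q the benefit rate among those excluded. Then the evaluable rate is (p − d·q)/(1 − d). The documents give neither d nor q; both are assumptions here.

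| d | p = 50%, q = 0 | p = 50%, q = 25% | p = 50%, q = 50% |
|---|---|---|---|
| 10% | 55.6% | 52.8% | 50% |
| 20% | 62.5% | 56.3% | 50% |
| 30% | 71.4% | 60.7% | 50% |

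The column q = 0 is the upper bound. The bias is zero when excluded patients benefit at the overall rate, or when nobody is excluded.

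**3. Chance of declaring activity when the rate in all treated patients is 5%.** Put the evaluable rate into the formula in step 1.

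| d | q = 0 | q = 2.5% |
|---|---|---|
| 10% | 0.184 | 0.166 |
| 20% | 0.232 | 0.189 |
| 30% | 0.297 | 0.220 |

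The comparison value is 0.148, and it stays 0.148 if H0 is defined in evaluable patients. At a true 50% CBR the drug is declared active with probability above 0.999 under either denominator.

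**4. Patients absent from the primary rate.** Treated patients needed for 28 evaluable = 28/(1 − d): 31.1, 35 and 40, so 32, 35 and 40 in whole patients. That leaves 4, 7 and 12 treated patients outside the primary rate.

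**The case against.** **The hypotheses may refer to evaluable patients.** Section 11.3 names evaluable patients and goes straight on to the 5% and 20% rates. On that reading the type I error is unchanged at 0.148. This stands, and it confines the main harm to the estimate. The text does not settle which reading is meant.

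**Excluded patients can be successes.** Section 10.4 measures stable disease from start of therapy to progression and does not require continued dosing; section 12.1 asks for investigations to continue after early stopping. A patient who stops for toxicity and is progression-free at week 12 would meet the SD criterion, yet section 10.1.2 leaves that patient out. This also stands: it makes the size of the bias uncertain, and q = 0 is only a ceiling. But benefit in such patients has to be documented after they leave treatment, so a benefit rate as high as in completers is unlikely.

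**Exclusions may be few.** Entry requires life expectancy above 24 weeks, and section 8.3 allows interruptions and up to three dose reductions before removal. That is fair, and 30% should not be read as a forecast. On the other side, section 8.3 lists several events that end treatment and could occur in the first 12 weeks.

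**Early failures remain visible elsewhere.** Overall survival, time to progression and toxicity are not limited to evaluable patients. True, but none of these corrects the primary rate.

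**Group (b) may be small.** Dosing in the second cycle ends at week 10 (4 + 2 + 4), so progression in weeks 11 to 12 might already count as after two cycles. This narrows the gap without closing it.

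**Conclusion.** The concern holds. Followed as written, section 10.1.2 removes from the primary denominator mostly patients without benefit, so CBR and overall response rate are biased upward as estimates for treated patients. The evaluable rate is valid for its own subset only. With 10% to 30% excluded, a true 50% CBR would read up to 56% to 71%, or 53% to 61% if excluded patients benefit at half the overall rate. These shares are assumptions; the direction rests on early stoppers benefiting less often than completers. The decision rule is affected only when the true rate is near the design range and only if the hypotheses describe all treated patients. Since the matter concerns the primary endpoint and the sections disagree on who is counted, it should be corrected before analysis.

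**What to change.** In sections 10.1.2 and 11.1 to 11.3:

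- Define the primary CBR population as all eligible patients who receive at least one dose. Section 7.2 already requires every criterion to be met at registration, so eligibility should remove nobody; judge it on baseline information only.
- Count patients without a qualifying post-baseline assessment as not benefiting. An early stopper with a qualifying assessment still counts as a success.
- Count the 14 and 28 in this population, and align sections 10.1.2, 10.2.5, 11.1 and 11.3.
- State that 5% and 20% refer to all treated patients, or restate the power.
- Keep the present evaluable set as a sensitivity analysis, and report the number excluded with reasons.

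At the least, extend the exception to progression, death, deterioration or discontinuation before the end of cycle 2.

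**Cost.** No new data: the treated set already exists for toxicity, and section 12.1 already asks for follow-up after early stopping. The reported rate will be lower. If 20% was meant for evaluable patients and excluded patients do not benefit, the all-treated rate is 20% × (1 − d) = 18%, 16% or 14% at 10%, 20% or 30% exclusion, and power with 28 treated falls from 0.915 to 0.873, 0.814 or 0.734. Restoring at least 0.915 with equal stages and the same cut-offs takes 32, 36 or 42 patients and raises alpha to 0.195, 0.245 or 0.322. Stating that the hypotheses refer to all treated patients is therefore the cheaper route.

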### 10.2 Response and Evaluation Endpoints

Response and progression will be evaluated in this study using the international criteria proposed by the RECIST (Response Evaluation Criteria in Solid Tumors) committee version 1.1 (Eisenhauer E, 2009).

#### 10.2.1 Measurable Disease.

Measurable tumour lesions are defined as those that can be accurately measured in at least one dimension (longest diameter to be recorded) with a minimum size of 10 mm by CT scan (CT scan thickness no greater than 5 mm), 10 mm caliper measurement by clinical exam or 20 mm by chest X-ray. Malignant lymph nodes considered to be pathologically enlarged and measurable, must be  $\geq$  15 mm in short axis when assessed by CT scan.

#### 10.2.2 Non-measurable Disease.

All other lesions (or sites of disease), including small lesions (longest diameter < 10 mm or pathological lymph nodes with  $\geq$  10 to < 15 mm short axis) as well as truly non-measurable lesions. Lesions considered truly non-measurable include: leptomeningeal disease, ascites, pleural/pericardial effusions, lymphangitic involvement of skin or lung, inflammatory breast disease, abdominal masses/abdominal organomegaly identified by physical exam that is not measurable by reproducible imaging techniques.

### 10.2.3 Target Lesions.

<sup>11 Day 1 assessments must be within 7 days prior to cycle day 1.

<sup>12At investigator discretion, frequency of CT imaging can be decreased from every 12 weeks to every 4 months (+/- 2 weeks) for patients receiving ongoing study treatment with responding or stable disease.

All lesions up to a maximum of 5 lesions total (and a maximum of two lesions per organ) representative of all involved organs should be identified as target lesions and will be recorded and measured at baseline. Target lesions should be selected on the basis of their size (lesions with the longest diameter), be representative of all involved organs, but in addition should lend themselves to reproducible repeated measurements. Pathological nodes, which are defined as measurable and may be identified as target lesions if the short axis is ≥ 15 mm by CT scan. A sum of the diameters (longest for non-nodal lesions, short axis for nodal lesions) will be calculated and reported as the baseline sum diameters. If lymph nodes are included in the sum, only the short axis is added into the sum. The baseline sum diameters will be used as reference to further characterize any objective tumour regression in the measurable dimension of the disease.

### 10.2.4 Non-target Lesions.

All other lesions (or sites of disease) including pathological lymph nodes should be identified as non-target lesions and should also be recorded at baseline. Measurements are not required but these lesions should be noted at baseline and should be followed as "present", "absent" or in rare cases "unequivocal progression".

### 10.2.5 RESPONSE

All patients will have their BEST RESPONSE on study classified as outlined below:

Complete Response (CR): disappearance of all target lesions. Pathological lymph nodes (whether target or non-target) must have reduction in short axis to < 10 mm.

Partial Response (PR): at least a 30% decrease in the sum of diameters of target lesions, taking as reference the baseline sum diameters.

Stable Disease (SD): steady state of disease. Neither sufficient shrinkage to qualify for PR nor sufficient increase to qualify for PD, taking as reference the smallest sum diameters while on study.

Progressive Disease (PD): at least 20% increase in the sum of diameters of target lesions taking as reference the smallest sum on study (includes baseline sum if that is smallest on study). In addition, the sum must also demonstrate an absolute increase of at least 5 mm. Appearance of new lesions will also constitute progressive disease. In exceptional circumstances, unequivocal progression of non-target lesions may be accepted as evidence of disease progression.

Response Criteria

Target	Non-Target	New	Overall	
Lesions	Lesions	Lesions	Response	
CR	CR	No	CR	
CR	Non-CR/Non-PD	No	PR	
CR	Not evaluated	No	PR	
PR	Non-PD or not all	No	PR	
	evaluated			
SD	Non-PD or not all	No	SD	
	evaluated			
Not all	Non-PD	No	NE	
evaluated				
PD	Any	Yes or No	PD	
Any	PD*	Yes or No	PD	
Any	Any	Yes	PD	

\* In exceptional circumstances, unequivocal progression in non-target lesions may be accepted as disease progression.

Note: Patients with a global deterioration of health status requiring discontinuation of treatment

without objective evidence of disease progression at that time should be reported as "symptomatic deterioration". Every effort should be made to document the objective progression even after discontinuation of treatment.

### **10.3 Response Duration**

Response duration will be measured from the time measurement criteria for CR/PR (whichever is first recorded) are first met until the first date that recurrent or progressive disease is objectively documented, taking as reference the smallest measurements recorded on study.

#### 10.4 Stable Disease Duration

Stable disease duration will be measured from the time of start of therapy until the criteria for progression are met, taking as reference the smallest sum on study.

#### 10.5 Methods of Measurement

The same method of assessment and the same technique should be used to characterize each identified and reported lesion at baseline and during follow-up.

- 10.5.1 Clinical Lesions. Clinical lesions will only be considered measurable when they are superficial and  $\geq 10$  mm diameter as assessed using calipers (e.g. skin nodules). For the case of skin lesions, documentation by colour photography including a ruler to estimate the size of the lesion is recommended. When lesions can be evaluated by both clinical exam and imaging, imaging evaluation should be undertaken since it is more objective and may also be reviewed at the end of the study.
- 10.5.2 Chest X-ray. Lesions on chest X-ray are acceptable as measurable lesions when they are clearly defined and surrounded by aerated lung. However, CT is preferable.
- 10.5.3 CT, MRI. CT is the best currently available and reproducible method to measure lesions selected for response assessment. CT should be performed with slice thickness of 5 mm or less. When CT scans have slice thickness greater than 5 mm, the minimum size for a measurable lesion should be twice the slice thickness. MRI is also acceptable in certain situations (e.g. for body scans).
- 10.5.4 Ultrasound. Ultrasound is not useful in assessment of lesion size and should not be used as a method of measurement. Ultrasound examinations cannot be reproduced in their entirety for independent review at a later date and, because they are operator dependent, it cannot be guaranteed that the same technique and measurements will be taken from one assessment to the next. If new lesions are identified by ultrasound in the course of the study, confirmation by CT or MRI is advised.
- 10.5.5 Endoscopy, Laparoscopy. The utilization of these techniques for objective tumour evaluation is not advised. However, such techniques can be useful to confirm complete pathological response when biopsies are obtained or to determine relapse in trials where recurrence following complete response or surgical resection is an endpoint.
- 10.5.6 Cytology, Histology. These techniques can be used to differentiate between PR and CR in rare cases (for example, residual lesions in tumour types such as germ cell tumours, where known residual benign tumours can remain). The cytological confirmation of the neoplastic origin of any effusion that appears or worsens during treatment can be considered if the measurable tumour has met criteria for response or stable disease in order to differentiate between response (or stable disease) and progressive disease.

### 10.6 Endocrine Response

24-hour urinary metanephrines, catecholamines and serum chromogranin A will be measured after the end of each 12 week cycle (ie. end of every two cycles). Subjects will be considered evaluable for endocrine response if they have completed at least one full cycle of treatment. An endocrine response will be as defined by a > 20% drop in one of the aforementioned parameters and sustained for >12-week period and will be considered a secondary endpoint of the trial.

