#### 2.0 BACKGROUND INFORMATION AND RATIONALE

Paragangliomas (PGs) are highly vascularized tumours that generally arise from the parasympathetic system in the head and neck, sympathetic ganglia in the thorax and abdomen, and the adrenal medulla. These latter tumors may be functional, secreting catecholamines (pheochromocytomas [PC]).

These tumors can arise as a result of germline mutations in RET, VHL, NF1, and in subunits B, C, or D of the succinate dehydrogenase (SDH) genes, which underlie multiple endocrine neoplasia Type 2 (MEN2), von Hippel–Lindau (VHL), neurofibromatosis Type 1 (NF1), and familial paraganglioma syndromes Type 4 (PGL4), 3 (PGL3), and 1 (PGL1), respectively. Global expression signatures of a large group of 76 hereditary and sporadic primary pheochromocytomas and paragangliomas have been generated. It was found that tumors with VHL and SDHB or D mutations form a single genetic expression cluster, which is distinct from "Cluster 2" pheochromocytomas: those with mutations in RET, NF1, and novel familial pheochromocytoma variants without a known primary genetic defect. In this series, sporadic pheochromocytomas were distributed between the two major clusters. Importantly, novel VHL or SDHB mutations were detected in tumors that aligned with Cluster 1, while RET or uncharacterized deletions were identified in tumors that segregated with Cluster 2 that had not previously been screened. A pathway-enrichment method, gene-set enrichment analysis (GSEA), was then applied to the data to delineate the underlying biological programs embedded in each of these clusters and this suggested that cluster 1 tumors were associated with hypoxia and angiogenesis pathways whilst cluster 2 tumors were associated with pathways representing abnormalities of protein synthesis and translation as well as kinase signalling.

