### 5.1 Inclusion Criteria

- 5.1.1 Histologically or cytologically confirmed diagnosis of malignant paraganglioma or pheochromocytoma and either evidence of metastases or unresectability.
- 5.1.2 Evidence of recent disease progression radiologically or biochemically or patients with problematic tumourrelated symptoms despite lack of documented recent radiological or biochemical progression
- 5.1.2.1 Radiological disease progression will be defined as follows; when any set of paired CT scans of the chest, abdomen and pelvis (done within 13 months of each other) are retrospectively reviewed and there is progression as evidenced by either any new lesions or at least a 20% increase in the sum of the LD (longest diameter) of target lesions (that will then go on to be followed in the trial), taking as reference the smallest sum LD recorded within the preceding 13 months.
- 5.1.2.2 Biochemical disease progression will be defined as follows; when rate of change equals or exceeds 50% increase over a 6 month +/- 1 month period of either or any of 24-hour urinary metanephrines, catecholamines or serum chromogranin A
- 5.1.2.3 Symptomatic criteria is intended to capture patients whose paraganglioma is clearly causing symptoms to patient or clinical signs concerning to the investigator despite the absence of prior documentation of radiological or symptomatic progression. This would include newly diagnosed patients with concerning signs or symptoms. Investigators will still attempt to document radiological or biochemical progression if possible, as many patients will meet several criteria.

Note: eligibility clarifications settled by PI.

- 5.1.3 Measurable disease defined as that which can be measured in at least one dimension (LD to be recorded) with a minimum size of 10 mm by CT scan
- 5.1.4 ECOG 0-2
- 5.1.5 Life expectancy of greater than 24 weeks.
- 5.1.6 Age > 18 years. (There are no dosing or adverse event data currently available on the use of sunitinib in patients < 18 years of age, therefore patients in this age group are excluded from this study)
- 5.1.7 Patients must have normal organ and marrow function
- 5.1.8 Patients must have PT/INR/PTT within 1.2 X the upper limit

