### The **secondary end points** will be as follows:

- 1. Biochemical response as defined by a > 20% drop in one of; 24-hour urinary metanephrines, catecholamines or serum chromogranin A, and sustained for > 12-week period
- 2. Overall survival
- 3. Time to progression
- 4. Overall response rate (PR) + (CR)
- 5. tumour symptom improvement (descriptive)

NB: Response is defined as per the RECIST criteria as a 30% decrease in the sum of the diameters of the target lesions (partial response) maintained for at least 4 weeks, or complete disappearance of disease and cancer related symptoms (complete response), also maintained for at least 4 weeks. The 95% confidence interval for response rate will be calculated. The median and range of the duration of response will be assessed.

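### Endocrine response requires no raised marker at baseline and compares every later value with what appears to be a single baseline, so patients with normal markers are counted and a sustained fall can arise by chance

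*Combined protocol and SAP*

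**What the plan says.** The endpoint is defined twice, consistently. Section 10.6: "An endocrine response will be as defined by a > 20% drop in one of the aforementioned parameters". The same sentence requires the fall to last more than 12 weeks and makes this a secondary endpoint. Section 11.2, first secondary endpoint: "> 20% drop in one of; 24-hour urinary metanephrines, catecholamines or serum chromogranin A, and sustained for > 12-week period".

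The evaluable set is wide: "Subjects will be considered evaluable for endocrine response if they have completed at least one full cycle of treatment". On treatment the markers "will be measured after the end of each 12 week cycle (ie. end of every two cycles"), that is, at about weeks 12, 24 and 36 for a patient who receives six cycles (section 12.2).

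Three things are not stated:

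- **A baseline level.** Section 6.0 schedules the three marker tests within 7 days of registration, with no threshold. Section 5.1.2 admits patients on radiological progression or symptoms alone. Section 2.0 says of tumours in the sympathetic ganglia and adrenal medulla: "These latter tumors may be functional, secreting catecholamines".
- **The reference value.** Neither section names it. Section 6.0 schedules one set of tests and no repeat, so a single baseline is the apparent reference.
- **How many low values make a fall sustained.** Tests 12 weeks apart span exactly 12 weeks, while the rule asks for more than 12.

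**The concern.** The endpoint is meant to show whether sunitinib lowers biochemical activity, which is a stated objective in section 1.0. Two features blur that.

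First, a patient whose markers are all normal at entry is still evaluable. Such a patient either adds a non-response that says little about the drug or scores on a fall within the normal range.

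Second, there are three markers, and each follow-up value is judged against the same baseline reading. If that reading happens to be high, all later values tend to look low together, so the duration condition filters out less chance variation than it seems to. With a single arm there is no control rate to subtract. A reported endocrine response rate would then be hard to attribute to the drug.

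**Working it through.** **Plan figure to reproduce.** There is none. The documents give no expected rate, power or marker variability for this endpoint.

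**Inputs from the documents.** A fall of more than 20%; any one of three markers; sustained for more than 12 weeks; tests every 12 weeks (10.6, 11.2); up to 28 response-evaluable patients (11.1).

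**Assumptions, not in the documents.** Log-normal within-person variation with CV 10% to 30%; between-marker correlation 0 or 0.5; one baseline reading; no true change; the same marker low at each required test; all required tests done.

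**Formula.** On the log scale the within-person SD is s = √ln(1 + CV²). A visit counts as low if its difference from baseline is below ln 0.8 = −0.223. That difference has SD s√2.

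**By hand at CV 20%, independent markers.**

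1. s = √ln 1.04 = 0.198, and s√2 = 0.280.
2. One marker, one test: Φ(−0.223/0.280) = Φ(−0.797) = 0.213.
3. Any of three markers, one test: 1 − (1 − 0.213)³ = 0.513.
4. One marker, two tests: the two differences share a baseline, so they correlate at 0.5. The joint probability is 0.095. If each test had its own independent reference it would be 0.213² = 0.045. The shared baseline roughly doubles it.
5. Any of three markers, two tests: 1 − (1 − 0.095)³ = 0.259. Simulation gives 0.260.

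**Chance response rates by simulation, no drug effect.** Where a range is shown, the lower end is correlation 0.5 and the upper end is correlation 0.

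| Rule | CV 10% | CV 20% | CV 30% |
|---|---|---|---|
| Any of three, one test (duration condition ignored) | 13–16% | 41–51% | 52–65% |
| Any of three, low at weeks 12 and 24 | about 4% | 21–26% | 32–39% |
| Any of three, two consecutive lows among weeks 12, 24, 36 | 6–7% | 29–35% | 41–51% |
| Any of three, low at all of weeks 12, 24, 36 | about 2% | 13–16% | 22–27% |
| One marker chosen without using the baseline reading, weeks 12 and 24 | 1% | 10% | 15% |
| Any of three, fall of at least 50%, weeks 12 and 24 | about 0% | 0.2% | 3% |

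For scale, the second row applied to 28 patients is about 1 (28 × 0.04), 6 to 7 (28 × 0.21 to 0.26) and 9 to 11 (28 × 0.32 to 0.39).

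**Choosing the marker by its baseline level.** Suppose each patient's marker is the one with the highest multiple of ULN at the reference baseline, among patients with at least one marker above ULN (independent markers, two tests). The chance rate is 5%, 25% and 38% at CV 10%, 20% and 30% if all true levels sit at ULN, much the same as the present rule. It is 2%, 12% and 21% if true levels are widely spread (log SD 1). Selecting on a high reading builds in regression to the mean.

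**Direction of the effect of normal-marker patients.** If a fraction f of evaluable patients have no raised marker and score at chance rate c, while the rest respond at rate r, the observed rate is (1 − f)r + fc. This is below r when c < r and above r when c > r. The documents give neither f nor r.

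**The case against.** The strongest reply is that the rule already has a safeguard. A reader who stops at the 20% threshold might infer that any single dip scores. It does not: the fall must be sustained for more than 12 weeks, and comparing the first table row with the others shows that this cuts the chance rate substantially. On the strictest reading, three low values, it is 13–16% at CV 20%. If the within-person CV is near 10%, the problem is small on every sustained reading. This stands, and it is why the size is given as a range.

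Other inferences go further than the documents allow:

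- *That one marker may be low at the first test and another at the second.* A drop in one parameter that is sustained naturally means the same parameter. A clarifying word is worthwhile, but this is not a defect.
- *That the plan itself treats 50% as the meaningful change.* Section 5.1.2.2 does say "when rate of change equals or exceeds 50% increase over a 6 month +/- 1 month period", but that is an eligibility rule for a rise. Undoing a 50% rise takes a 33% fall (1 − 1/1.5), not 50%. Thresholds that differ by direction are also normal here: section 10.2.5 uses 30% down and 20% up.
- *That patients with non-functional tumours have nothing to suppress.* Section 2.0 speaks only of catecholamine secretion. No section ties chromogranin A to functional status.
- *That the bias is only upward.* Normal-marker patients can also dilute a true effect. So can patients who stop after one cycle: they are evaluable but cannot show a sustained fall before about week 24.

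It can also be said that no test or decision rests on this endpoint and that the raw values allow other tabulations later. That is true, but a definition fixed beforehand carries more weight than one chosen at reporting.

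**Conclusion.** The point holds in a limited form. As written, the endocrine response rate includes patients with no raised marker and can credit falls that come from one high baseline reading. With no drug effect and two follow-up tests, about 4%, 21–26% and 32–39% of patients would score at within-person CVs of 10%, 20% and 30%; with three required low values, about 2%, 13–16% and 22–27%. These figures rest on assumed CVs, assumed between-marker correlations and a single baseline. They apply to patients who reach the required tests.

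A reader might infer that the trial's main conclusion is at risk. It is not: the primary endpoint in section 11.2 is clinical benefit rate and the accept/reject rule in section 11.3 uses it. The effect is confined to a secondary endpoint.

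**What to change.** Amend sections 10.6 and 11.2:

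1. Make the evaluable set patients with at least one marker above ULN at baseline, and count response only in a marker that was raised at baseline.
2. State that two consecutive 12-weekly tests in that same marker satisfy the duration condition.
3. Report the proportion with a sustained fall of at least 50% alongside the 20% rule, without presenting it as the counterpart of 5.1.2.2.
4. Do not choose a patient's marker by the highest multiple of ULN at the baseline that also serves as reference. Where an earlier pre-study value exists, use it to choose the marker and keep the registration value as the reference. The chance rate is then about 1%, 10% and 15% at CV 10%, 20% and 30% with two tests. Where no earlier value exists, steps 1 to 3 apply alone.

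The cost is wording only. The on-study values are already scheduled, and patients entering under 5.1.2.2 must already have serial pre-study values. The downside is a smaller denominator. Step 1 alone also does not remove regression to the mean, because requiring a raised reading favours high ones. For the same reason, the rates in step 4 assume that the registration value plays no part in selection; where it also decides who counts as raised, they can be exceeded for markers whose true level is near ULN. The report should say so.
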